10.3. Level of significance and power

A two-sided significance level of 5% will be applied. For a description of the power see section 10.2 above.

10.4. Pass/fail criteria

The purpose of the investigation is fulfilled if a **statistically significant** improved difference in the primary endpoint is obtained with the test product compared to [REDACTED]

11. Data management

11.1. Data collection and data management

11.1.1. Data Collection in the clinical investigation

Data management and statistical analyses are carried out by [REDACTED] Coloplast A/S.

Data will be collected through an electronic data capturing (EDC) system on electronic Case Report Forms (eCRF), a secure, internet-based case report form. This system will be used to record all subject information collected in the investigation for secure data tracking and centralised data monitoring ("remote monitoring") done by monitors, as defined in the monitoring plan.

The EDC system used is [REDACTED], delivered by [REDACTED] system is designed to be compliant with the FDA requirements of 21 CFR part 11. It is a validated data management system allowing only qualified and trained personnel to enter the system. The system has full audit trail and electronic signature.

The sponsor will be responsible for training the Principal Investigator, or designee, in completion of the eCRF.

Principal Investigator, or delegate, at the clinical site will perform primary data collection directly into the eCRF or drawn from source document (medical records) reviews. The eCRF will be completed on a continuous basis starting from the point of enrolling the subject to final follow up.

The eCRF will be completed by the investigator, or delegate, who have signed the Site Personnel Signature and Delegation List and Clinical Investigation Training Log. It will be the responsibility of the Principal Investigator, or designee, to ensure that all measurements and observations are correctly noted in the eCRF.

All assessments and observations throughout the investigation for each subject must be carefully recorded in an eCRF during the visit or immediately after. The eCRF makes it possible to enter data right away when they are obtained. This is the preferred way of collecting data. In case this is not possible the data should be entered no later than 7 days after the visit / procedure.

The DLQI questionnaire will be completed by the subject and entered into the eCRF by site personnel.

Adverse events should be registered following the timelines described in the Adverse Event section.

The subject will receive an iPhone with the Clinical Trial App installed. The app is developed on behalf of Coloplast A/S by the app development company Nodes. This Clinical Trial App is used during the investigation every time the subject makes a product (1-piece) or baseplate (2-piece) change.

The photos and the data completed in the Clinical Trial App are transferred via an encrypted connection to a Coloplast controlled [REDACTED] environment. Photos will be stored and can be assessed at [REDACTED]. All other data will be transferred automatically into the EDC system.

Additional data from other apps or external companies will be batch loaded into the EDC system.

In the unforeseen situation, where site cannot establish connection to the EDC system a paper CRF (pCRF) has been printed and supplied by sponsor.

The Principal Investigator will keep a separate list of the subjects' ID numbers, enrolment date, randomisation number, date of birth, names, phone number, email and addresses in a locked room/cabinet. Only data referred to in this clinical investigation plan will be recorded in the CRFs.

11.1.2. Database Management, Queries and Quality Control

The data management system has restricted role-based access control. The Principal Investigator, or designee must be trained in the system prior to getting access. The training is web-based and must be completed before access to the investigation is granted. Training will be documented in the data management system. Only the Principal Investigator, or designee, will be authorised to enter data in the eCRF.

The monitor, using his/her personal login information shall verify all critical data points against the source documents and issue electronic queries for the authorised clinical site personnel to respond, as defined in the monitoring plan.

The Principal Investigator, or designee, using his/her personal login information shall sign each eCRF.

Automated, real time access to the data enable control on study compliance and safety assessments.

A critical quality control will be performed by the sponsor's data management team and queries issued where needed. Such queries will be reviewed by the monitor and must be resolved by the site personnel.

At the end of the study a formal data review meeting will be performed before the database will be locked.

A full audit trail ensures, that each user's (site personnel, monitor, sponsor, data manager) access to and actions in the system is tracked.

The Data Management Procedures are further described in the Data Management SOPs.

11.2. Data retention

All investigation site documents must be archived for a minimum period of 10 years after the final clinical investigation report has been signed. The monitor is responsible for informing the investigator and the CM if this period should be longer for their sites according to local regulation.

12. Amendments to the Clinical Investigation Plan

No changes in the clinical investigation procedures shall be affected without mutual agreement between the Principal Investigator and the sponsor. The agreement of the changes must be documented by signing the corresponding clinical investigation plan amendments and registered in the Change Log.

All significant changes require notification to the EC and applicable regulatory authority. Substantial changes may require approval from the EC and applicable regulatory authority prior to implementation.

13. Deviations from the Clinical Investigation Plan

Deviations to the Clinical Investigation Plan occurs when the activities during the clinical investigation do not comply with the EC and CA approved investigation plan.

A minor deviation is defined as those that do not increase risk or decrease benefit or do not have a significant effect on the subject's rights, safety, or welfare; and/or on the integrity of the data. If a deviation increases risk or decreases benefit and/or; has a significant effect on the subject's rights, safety, or welfare and/or has a significant effect on the integrity of the data it is defined as a major deviation and the Investigator must inform the monitor immediately, and the Monitor will report and inform the Clinical Manager or designee immediately.

The investigator is not allowed to deviate from the Clinical Investigation Plan unless, under emergency circumstances or to protect the rights, safety, and well-being of the subject(s).

For the purposes of this investigation, any variance from the protocol is considered a deviation and is to be reported.

The site will complete a deviation eCRF for all data-related deviations and all deviations that are not related to the data (for example, an untrained nurse performing study procedures) are reported by the monitor in the periodic monitoring report and any actions for additional follow up are addressed with the Investigator.

If any deviations to the investigation plan are detected during the monitoring visit, the Monitor shall ensure the site reports all deviations in the eCRF or on the Deviation log in the Investigator File. Additionally, the monitor must report any deviation noted during the visit in the Periodic Monitoring Report.

Monitor will align with data management in each investigation, how data management will be informed about all deviations.

Details about the deviation will be collected, for example:

- Site ID
- Subject ID
- Deviation Date
- Clear and concise description of the event
- The reason for the deviation and any corrective action taken, including the date of the corrective action.

If applicable, record the EC notification date and retrieve a copy of the EC Submission Letter for the eTMF.

14. Device Accountability

All access to the investigational devices used in the clinical investigation is controlled by storage procedures and device accountability logs as described below. The investigational devices must only be used in this clinical investigation and only according to the CIP.

Sponsor keeps a device accountability log that states the physical location of all investigational devices from shipment of investigational devices to the investigational sites until return of or disposal.

The PI, or designee, keeps records documenting the receipt, use and return and disposal of the investigational devices, which includes:

- Name of the product received
- Date of receipt.
- Identification of each investigational products (batch no./lot no.)
- Number of products received
- Number of products distributed to subject
- The date(s) of use
- Subject identification
- The date on which the investigational product was returned/explanted from the subject
- The date of return unused, expired or malfunctioning investigational products to Sponsor

15. Statement of compliance

The clinical investigation is conducted in accordance with:

- Ethical principles that have their origin in the Declaration of Helsinki, 1964, Last amended at the 59th WMA General Assembly, Brazil, October 2013.
- MDD 93/42/EEC as amended by Directive 2007/47/EC (commonly known as the Medical Device Directive).
- MDR (EU) 2017/745
- ISO 14155:2020 "Clinical Investigation of medical devices for human subjects – Good clinical practices".
- Any applicable regional or national regulations will be specified in the country specific CIP.

15.1. Ethics committee and regulatory authorities

The CIP and/or other relevant documents are submitted to the appropriate EC(s) and regulatory authorities. This clinical investigation will not begin until the required approval from the EC and regulatory authorities have been obtained. Any amendment to the clinical investigation plan will be submitted to the same EC(s) and regulatory authority. Sponsor will notify the relevant regulatory authority and EC(s) concerned of the end of the clinical investigation.

15.2. Data protection

As part of the investigation Coloplast A/S, [name] ("Coloplast") will collect and process personal information provided by the subject for the investigation ("subject personal data"). This includes identification and contact information, which will be pseudonymized. Prior to visit 1, the subject will be randomised to either treatment Arm A or B and will be allocated a randomisation number, as well as information about the subject's product usage experience and health. Coloplast will comply with the EU General Data Protection Regulation (GDPR) and the Danish act on data protection ("databeskyttelsesloven"), including in connection with transfer of data to third countries, cf. chapter V of GDPR, Coloplast will only process the subjects' personal data:

1. To conduct the investigation and carry out related research based on subject consent (primary use), cf. articles 6(1)(a) and 9(2)(a) of GDPR,
2. To comply with applicable legal obligations to e.g., ensure reliability and safety, cf. article 6(1)(c) in conjunction with article 9(1)(i) of GDPR, and
3. If separate consent is given for secondary use of subject personal data, cf. articles 6(1)(a) and 9(2)(a) of GDPR – carry out research outside the clinical protocol to improve Coloplast's products and services, and for use in education.

Part of Coloplast's processing is carried out on third-party platforms (clinical trial databases) and certain third parties are assisting Coloplast in the processing (e.g., the Principal Investigator, or designee). Such cases will imply a transfer of personal data to the third parties, but solely for the specified purposes and with the third

parties acting on instruction from Coloplast. Data may be collected and processed across the Coloplast network, which may entail processing of personal data outside the European Economic Area. In such cases, an adequate level of protection will be ensured by the third parties being subject to the standard contractual clauses on data protection adopted by the EU or to an EU-approved certification mechanism on data protection. For further information about this please the subject can always consult Coloplast's data protection officer (details below).

Subject personal data will be kept as long as required under applicable laws and regulations. The EU Medical Device Regulation obligates Coloplast to keep the data for a period of at least ten years after the investigation is completed, or, in the event that the device is subsequently placed on the market, at least ten years after the last device has been placed on the market. Subject personal data will be deleted at the end of the mandatory retention period.

If the subject has questions or queries regarding Coloplast's handling of personal information, the subject can always contact Coloplast's Data Protection Officer at [REDACTED]. Complaints related to Coloplast's handling of subject personal information may similarly be sent to the Data Protection Officer, and the subject is also entitled to file a complaint with the relevant supervisory authority, which in the case of Denmark is the Danish Data Protection Agency (www.datatilsynet.dk).

The subject can write to [REDACTED] at any time to request:

- Access to personal data
- Correction of errors in personal data or to erase personal data
- Limit what can be done with personal data
- To receive personal data in machine-readable format (data portability).
- Withdrawal of consents the subject has given Coloplast to process personal data

15.3. Indemnity

All subjects are fully covered by Coloplast A/S insurance throughout the investigation.

15.4. Financial conditions

Coloplast A/S will compensate all investigators involved in the clinical investigation for their time and resources spent on the investigation. All financial agreements with the investigation sites involved in the clinical investigation will be specified in a sponsor investigator contract.

16. Informed consent process

Written informed consent is obtained from all subjects participating in the investigation after thorough written and verbal information. The information is given by the investigator or his/her representative in the subjects' native non-technical language. Each subject will be fully informed about the aim of the investigation, procedures, potential risks, or inconveniences and/or expected benefits and ensure ample time is provided before deciding on participation. The subjects will be informed that their participation is voluntary and that they may leave the investigation at any time, without this having any influence on their further treatment.

The informed consent signature form includes personally dated signatures of the subject and the PI, or designee. A copy will be provided to the subject.

If new information is to be given during the investigation, sponsor will inform the investigators, and the new information is given to the subjects by the investigator. If new information becomes available that can significantly affect a subject's future health and medical care that information will be provided to the subject in written form. CM is responsible for writing the information and providing it to investigators that will further provide it to the subjects. If applicable, all affected subjects shall be asked to confirm their continuing informed consent in writing.

This procedure also applies to informed consent obtained from a subject's legal representative. The procedure cannot waive the subjects' legal rights.

17. Subject compensation

17.1. Compensation in case of injury

Product liability and No-Fault Clinical Investigation Insurance covering the duration of the clinical investigation are in place, to enable compensation in the event of an injury to a participating subject.

17.2. Compensation for participating in the clinical investigation

If applicable, subjects will be compensated for their participation in the clinical investigation.

Subject payment/subject/visit

18. Adverse events, adverse device effects and device deficiencies

18.1. Adverse events

An adverse event is any untoward medical occurrence, unintended disease or injury, or untoward clinical signs (including abnormal laboratory findings) in subjects, users, or other parties, whether or not related to the medical device(s), or the procedures involved. This could include events such as headache or dizziness.

18.2. Adverse device effect

An adverse event, which is related to the use of the investigational medical device, is an adverse device effect, and should be marked as related or possibly related on the adverse event form.

The definition of an adverse device effect includes any event resulting from insufficiencies or inadequacies in the instruction for use, or any malfunction of the medical device, as well as any event resulting from use error or from intentional misuse of the device.

Temporary redness upon removal of the baseplate is not considered to be an adverse device effect. However, an abnormal development in the intensity or duration of redness should be considered an adverse device effect. A development in redness after removal of the baseplate is considered abnormal, when the intensity of redness is not decreased after five-ten minutes after the baseplate has been removed.

18.3. Device deficiency

A device deficiency is the inadequacy of the investigational device or comparator with respect to its identity, quality, durability, reliability, safety, or performance. This includes malfunctions, use errors and inadequacy in the information supplied by the manufacturer including labelling.

18.4. Serious adverse events (SAE)

A serious adverse event is an adverse event that:

- Led to death,

- Led to a serious deterioration in the health of the subject, users or other persons as defined by one or more of the following:
 - 1) a life-threatening illness or injury, or
 - 2) a permanent impairment of a body structure or a body function including chronic diseases, or
 - 3) in-patient or prolonged hospitalization, or
 - 4) medical or surgical intervention to prevent life-threatening illness or injury or permanent impairment to a body structure or a body function.
- Led to fetal distress, fetal death or a congenital abnormality or birth defect.

This includes device deficiencies that might have led to a serious adverse event if:

- Suitable action had not been taken, or
- Intervention had not been made, or
- Circumstances had been less fortunate.

These are handled under the serious adverse event reporting.

Planned hospitalization for a pre-existing condition, or a procedure required by the CIP, without serious deterioration in health, is not considered a serious adverse event.

18.4.1. Serious adverse device effect (SADE)

A serious adverse device effect is an adverse device effect that has resulted in any of the consequences characteristic of a serious adverse event.

18.4.2. Anticipated serious adverse device effect (ASADE)

Anticipated serious adverse device effect is any event that by its nature, incidence, severity, or outcome has been previously identified in the risk analysis report.

18.4.3. Unanticipated serious adverse device effect (USADE)

An unanticipated serious adverse device effect is a serious adverse device effect which by its nature, incidence, severity, or outcome has not been identified in the current version of the risk analysis report.

18.5. Medical care of subjects

Principal investigator shall ensure that adequate medical care is provided to a subject experiencing an adverse event during and after participation in the clinical investigation. All serious adverse events will be followed until a resolution is addressed.

The current status of all ongoing adverse events is documented during site close-out.

18.6. Reporting and timelines

All adverse events and device deficiencies will be reported in the eDC, [REDACTED] database. If, for some reason, the system is off-line, investigators (or designee) are required to report the event to: [REDACTED]

18.7. Investigator's reporting responsibilities

PI at each site must assess all (S)AE's that occur at his/her site.

- All serious adverse events and serious adverse device effects must be reported to sponsor within 24 hours of the site becoming aware of the event.
- A device deficiency that could have led to a serious adverse event but did not because suitable action was taken, intervention had been made or because of fortunate circumstances should be reported to sponsor within 24 hours of the site becoming aware of the event.

- New findings and/or updates in relation to already reported serious events should also be reported to sponsor within 24 hours of the site becoming aware of the event.
- Device deficiencies and all adverse device effects must be reported to sponsor within 10 days of becoming aware of the event.

When reporting the SAE, the relationship to the test material shall be described whether the event is considered

- **Not related**, the event has no temporal relationship with the use of the test material or the procedures.
- **Unlikely related**, the relationship with the use of the test material seems not relevant and/or the event can be reasonably explained by another cause, but additional information may be obtained.
- **Possibly related**, the relationship with the use of the test material is weak but cannot be ruled out completely. Alternative causes are also possible (e.g., an underlying or concurrent illness/ clinical condition or/and an effect of another device, drug, or treatment). Cases where relatedness cannot be assessed, or no information has been obtained should also be classified as possible.
- **Probably related**, the relationship with the use of the test material seems relevant and/or the event cannot reasonably be explained by another cause, but additional information may be obtained.
- **Definitely related/Causal relationship**, the event has a temporal relationship with the test material use/application or procedures.

The investigator will assess intensity for each AE and SAE reported during the investigation and assign it to one of the following categories:

- **Mild**, the intensity of the event is mild with no further action or intervention
- **Moderate**, the intensity of the event will lead to an action or intervention to solve the event
- **Severe**, the intensity of the event will lead to follow up on the action or intervention, as the effect of the action or intervention may not decrease the symptoms.

All above events must be reported by use of the relevant adverse event/serious adverse event/device deficiency form.

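### In section 18.7 the top SAE causality level requires only timing and the bottom level its absence, so a coincidental SAE during product use can meet both *Definitely related* and *Unlikely related*

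*Combined protocol and SAP*

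**What the plan says.** Section 18.7 asks the investigator, when reporting an SAE, to place its relationship to the test material on one of five levels:

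1. *Not related*: "the event has no temporal relationship with the use of the test material or the procedures".
2. *Unlikely related*: the relationship "seems not relevant and/or the event can be reasonably explained by another cause", with room for further information.
3. *Possibly related*: the relationship is weak but not excluded, and other causes are conceivable. This level also holds the only default rule: "Cases where relatedness cannot be assessed, or no information has been obtained should also be classified as possible".
4. *Probably related*: "the relationship with the use of the test material seems relevant and/or the event cannot reasonably be explained by another cause", again with room for further information.
5. *Definitely related/Causal relationship*: "the event has a temporal relationship with the test material use/application or procedures".

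The plan does not define a temporal relationship. It gives no order of precedence and does not say that the levels exclude one another.

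Relatedness is then used in four places. Under section 18.2 an event related to use of the device is an adverse device effect (ADE) and "should be marked as related or possibly related on the adverse event form". Section 18.4.1 builds on this: "A serious adverse device effect is an adverse device effect that has resulted in any of the consequences characteristic of a serious adverse event". Section 18.4.3 makes a SADE unanticipated if it "has not been identified in the current version of the risk analysis report". Section 18.9 opens by sending every SAE to the Medical Advisor, but its itemised list names only SAEs related to the product or the investigation, plus SADEs.

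**The concern.** An ordered causality scale should become more demanding as it rises. Here the highest level asks for less than the one beneath it: *Probably related* looks at relevance and at other explanations, while *Definitely related* looks at timing alone. At the other end, timing alone is enough to rule out *Not related*.

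In a trial where a study product is worn in both periods, timing separates events poorly. An SAE with an evident unrelated cause can begin while a product is on the skin. An investigator who follows the definition could grade it *Definitely related*; one who follows the label would not. With up to 10 sites in five countries, the same kind of event could be graded differently by site. At stake is whether an SAE is counted as device-related, and so as a SADE or USADE.

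**Working it through.** The plan states no figure to reproduce. The check is a reading of the five definitions against one another.

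**Inputs.** The definitions are those of section 18.7. Exposure comes from sections 4.8 and 5.8: two consecutive periods of about 35 days, so 35 + 35 = about 70 days. The schedule in section 7.5 records adverse events from Visit 1, the visit at which the first product is handed out.

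**Step 1: the test case.** Take an SAE with onset during wear, no relevant link to the product, and a reasonable other cause. Assume that onset during wear is a temporal relationship.

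- *Not related*: not met, because timing is present.
- *Unlikely*: met. Both limbs hold, so it does not matter whether and/or is read as *and* or as *or*.
- *Possibly*: not met. The relationship is not merely weak, and the event can be assessed, so the default does not apply.
- *Probably*: not met, because neither limb holds.
- *Definitely*: met, because timing is its only criterion.

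The event meets levels 2 and 5, three levels apart.

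**Step 2: is the test case isolated?** With timing present, cross relevance (relevant, weak, not relevant) with another reasonable cause (yes, no). This gives 3 × 2 = 6 combinations.

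| Relevance | Other cause | Levels met, and/or as *or* | Levels met, and/or as *and* |
|---|---|---|---|
| relevant | yes | 2, 4, 5 | 5 |
| relevant | no | 4, 5 | 4, 5 |
| weak | yes | 2, 3, 5 | 3, 5 |
| weak | no | 3, 4, 5 | 5 |
| not relevant | yes | 2, 5 | 2, 5 |
| not relevant | no | 2, 4, 5 | 5 |

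Read as *or*, 6 of 6 combinations meet at least two levels, and 4 of 6 meet both 2 and 5. Read as *and*, with *Possibly* taken to need an alternative cause, the counts are 3 of 6 and 1 of 6. If *Possibly* needs only a weak relationship, the first of these becomes 4 of 6. The combination that meets exactly levels 2 and 5 under both readings is the test case.

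**Step 3: does anything settle the conflict?** The default to *Possibly* covers only events that cannot be assessed or lack information. Section 18.2 names relatedness without mapping it to the five levels. Nothing else in section 18 ranks the levels.

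**Step 4: what depends on the grade?** SADE and USADE status depend on relatedness (sections 18.2, 18.4.1, 18.4.3), as does the related-SAE item in section 18.9. Reporting to the sponsor within 24 hours (18.7) and to authorities within 7 days (18.8) covers all SAEs. Section 18.5 follows all SAEs. The efficacy analysis and the pass/fail criterion (10.1.2, 10.4) do not use the grade, and section 10.1.5 does not prescribe a summary by relatedness.

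**The case against.** The strongest reply is the label. The level is named as a causal relationship, and a sensible investigator would not give it to an event with an obvious other cause. Section 18.2 also speaks of events resulting from the device. This shows what was intended and will prevent some misgrading. It does not mend the definition, which is the text that sites are given to apply.

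A second reply is that the five levels are introduced for SAEs only, and that the ADE, SADE and USADE definitions refer to relation to the device, not to a grade under section 18.7. The first half stands: non-serious events are outside this point. On the second half, the link is an inference, but section 18.7 contains the only graded relatedness scale in the plan, so a serious event would naturally be classified from it.

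A third reply is that the error over-attributes events to the device, which is the cautious direction, and that little follows from the grade. Much of this stands. Over-attribution is still a wrong classification, and it can differ by site.

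A reader might infer that nearly every SAE on study would be misgraded. The documents do not support that: they give no expected SAE count, and a narrower understanding of temporal relationship would reduce the overlap. Nor are the counts in the grid a magnitude. They are combinations of criteria, not events, and the larger ones depend on reading and/or as *or*. A reader might also infer that the Medical Advisor would miss SAEs graded as unrelated. The opening sentence of section 18.9 provides for all of them, so its narrower list is at most in tension with that sentence.

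**Conclusion.** The point holds as a defect of wording with a limited reach. As written, *Definitely related* is looser than *Probably related*, and a coincidental SAE during product use meets levels 2 and 5 at once while being barred from level 1. This rests on one assumption, that onset during wear counts as a temporal relationship. It does not rest on how and/or is read.

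The consequence is confined to the relatedness grade of SAEs, to which of them are classed as SADE or USADE, and to the related-SAE item in section 18.9. Safety reporting, SAE follow-up and the efficacy conclusion are not at risk. The number of events affected cannot be derived. The change is worth making because a rule that gives a wrong grade when followed literally can be corrected cheaply.

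**What to change.** Reword section 18.7 so that the two end levels match their labels and each event fits one level:

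- *Definitely related*: require a temporal relationship, a relevant relationship and no other reasonable cause, with no further information needed. The last condition separates it from *Probably related*.
- *Not related*: also cover an event that occurs during use but is clearly due to another cause.
- *Unlikely* and *Probably*: replace and/or with wording that does not overlap. Using *and* alone would leave the three combinations that now meet only level 5 without a clear level once that level is tightened (relevant with another cause, weak with none, not relevant with none). The text should therefore say where these go. Placing them in *Possibly* is one option, and the choice is the sponsor's.
- *Possibly*: keep it as the default for events that cannot be assessed.
- Section 18.2: add a sentence stating which of the five levels count towards the marking of an adverse device effect. The adverse event form may already do this, but it is not among the documents.

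The cost is a small text amendment handled under section 12, with ethics committee and authority notification if it is judged significant, and matching text on the SAE form and in site training. No visits, subjects or new data items are needed. A formal decision algorithm or a separate grade for each product is not required.
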